## OBJECTIVES

### 1.1.1 Title: Idelalisib for IgM-Associated AL Amyloidosis

### 1.1.2 Study Design:

This is a single arm, open label study designed to evaluate the safety and efficacy of idelalisib in patients with relapsed IgM-associated AL amyloidosis. Treatment will be comprised of idelalisib at 100mg orally twice daily, with permitted dose modifications for toxicity per manufacturer guidelines (Section 5). The medication will be continued until progression or significant toxicity.

After giving written informed consent, subjects will be evaluated for eligibility for enrollment in the study. Baseline evaluations will be performed as outlined in Section 7. Subjects who satisfy all inclusion and exclusion criteria will begin the study drug. Subjects will be monitored every cycle for safety and hematologic status. Organ function will also be measured during therapy.

Participants will be eligible to continue therapy as long as they do not demonstrate progressive disease or unacceptable toxicity. Standard response criteria for AL amyloidosis hematologic and organ response will be used (Gertz et al. 2010). Hematologic response will also be categorized and reported by Waldenstrom's macroglobulinemia hematologic response criteria. For the purposes of defining progressive disease, the amyloid response criteria will be used. Overall response rate will be measured and participants will be categorized into complete response, very good partial response, partial response and progressive disease. Progression free survival, organ response, safety and tolerability of idelalisib, and quality of life will be assessed.

### 1.1.3 Patient population: (Specific inclusion and exclusion criteria are detailed in section 3)

### 1.1.4 Number of sites: 1, Boston Medical Center, [name]

### 1.1.5 Number of patients: 18 patients

### 1.1.6 Primary Objective:

- To determine the hematologic overall response rate (ORR) in IgM associated AL amyloidosis to a fixed dose of idelalisib. Response rates will categorized into complete response (CR), very good partial response (VGPR), partial response (PR) and progressive disease (PD) according to standard criteria (Gertz et al. 2010).

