### **4.1.1 Agent Administration**

#### **4.1.1 Idelalisib**

Idelalisib will be administered orally at a dose of 100 mg (one tablet) twice daily. At 3 month visit, if the patient has no toxicities grade 2 or greater that are attributable to idelalisib, dose escalation to 150 mg PO BID is allowed at investigator discretion. Participants will be treated until progression, unacceptable toxicity, or decision to withdraw from the trial. Dose reductions due to toxicity will be permitted, according to dose modification instructions (Section 5).

The study drug idelalisib will be self-administered, and participants will be instructed to write in a diary daily, documenting that the drug was taken. Participants will be instructed to take the study drug at approximately the same time each day. If a dose is missed, it can be taken up to 6 hours after the scheduled time with a return to the normal schedule the following day. If it has been greater than 6 hours, the dose should not be taken and the patient should take the next dose at the scheduled time the next day. The missed dose will not be made up and must be returned to the site at the next scheduled visit; this must be documented in the study diary. Furthermore, they will be instructed to call the PI or research nurse if vomiting occurs. If the pills are vomited a replacement dose should not be taken that day. All dosages prescribed and dispensed to the participant, and all dose changes during the study must be recorded.

Drug accountability will be done at each study visit; unused drug and diaries will be collected from the participant, unused drug will be counted and returned to the pharmacy to be destroyed. A new prescription for either one cycle or three cycles, will be filled by the participant.

Medication labels will comply with US legal requirements and be printed in English. The storage conditions for study drug will be described on the medication label.

Idelalisib will be provided by Gilead Sciences, Inc. Idelalisib is formulated as tablets for oral administration and will be available for this study in 150-mg tablets or 100-mg tablets.

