Neutropenia	ANC 1.0 to <1.5 Gi/L	ANC 0.5 to <1.0 Gi/L	ANC <0.5 Gi/L
	Maintain Idelalisib dose.	Maintain Idelalisib dose. Monitor ANC at least weekly.	Interrupt Idelalisib. Monitor ANC at least weekly until ANC $\geq$ 0.5 Gi/L, then may resume Idelalisib at 100 mg BID (or if taking 150mg BID, decrease to 100mg).
Thrombocytopenia	Platelets 50 to <75 Gi/L	Platelets 25 to <50 Gi/L	Platelets <25 Gi/L
	Maintain Idelalisib dose.	Maintain Idelalisib dose. Monitor platelet counts at least weekly.	Interrupt Idelalisib. Monitor platelet count at least weekly. May resume Idelalisib at 100 mg BID (or if taking 150mg BID, decrease to 100mg) when platelets $\geq$ 25 Gi/L.

Abbreviations: ALT, alanine aminotransferase; AST, aspartate aminotransferase; ANC, absolute neutrophil count; BID, twice daily; ULN, upper limit of normal

Dose re-escalations will not be permitted once dose reduced to next lower dose level. If a participant requires a dose delay of 28 days or more, then the participant must be discontinued from the study.

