### **12.0 STATISTICAL CONSIDERATIONS**

This is a single arm, open label study designed to evaluate the safety and efficacy of idelalisib in IgM-associated AL amyloid patients. Patients will receive treatment until progression or unacceptable toxicity. Treatment will be comprised of idelalisib at 100 mg orally twice daily.

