## 12.2 Sample Size/Accrual Rate

We assume a total of 6 patients per year for 4 years meeting inclusion/exclusion criteria, with approximately 60% enrollment for a total of 15 patients. Using an optimal 2-stage design, we assume  $\alpha=.05$ ,  $p_0 = .05$  and  $p_1 = .25$ , where  $p_0$  and  $p_1$  are the response probabilities under the null and alternative hypotheses, respectively. Then we would have 80% power to detect a statistically significant response rate with 9 patients enrolled in Stage 1, proceeding to 9 patients enrolled in Stage 2 only if at least one patient has a response during the first stage. Using this design the intervention would be declared successful if at least a total of 3 responses are observed during the study period.

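### The primary objective concerns response to a fixed dose, but the treatment plan permits escalation to 150 mg BID at the 3 month visit and the success rule counts responses at either dose

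*Combined protocol and SAP*

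**What the plan says.** Section 1.1.6 states the primary objective: "To determine the hematologic overall response rate (ORR) in IgM associated AL amyloidosis to a fixed dose of idelalisib". It gives no milligram figure. That figure comes from Section 1.1.2, which sets 100 mg twice daily and allows modification for toxicity only, and from Section 12.0: "Treatment will be comprised of idelalisib at 100 mg orally twice daily".

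The treatment plan goes further. Under Section 4.1.1, at the 3 month visit, "dose escalation to 150 mg PO BID is allowed at investigator discretion", on the condition "if the patient has no toxicities grade 2 or greater that are attributable to idelalisib". Response status is not a condition. The dose modification table in Section 5 repeatedly provides for patients on the higher dose ("or if taking 150mg BID, decrease to 100mg").

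Under Section 12.2, "the intervention would be declared successful if at least a total of 3 responses are observed during the study period". Section 12.4 puts all eligible enrolled participants in the main response analysis, and Section 12.3 rules out stratification. Nothing limits the count to a dose or to a time before escalation, and no analysis by dose is planned. Section 12.1 words the primary endpoint as the response rate of idelalisib, without a dose.

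**The concern.** The objective names one treatment condition and the treatment plan delivers another. An increase offered to patients who tolerate the drug well is not a modification for toxicity, so the allowance in Section 1.1.2 does not cover it.

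This reaches the primary analysis because the response count stays open after the point of escalation. Under the calendar in Section 7, free light chains are measured at months 1 and 2 and then every three months. Section 4.1.4 anticipates up to 2 years per patient. Any assessment after the 3 month visit can fall on either dose. Patients reach the higher dose through tolerance and investigator choice, so they are a selected group.

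The threshold is only 3 responses, so a single responder after escalation can decide the result. The trial could then be reported as showing activity at a fixed dose when part of the evidence came from a higher one. Section 2.1.8 says that most available efficacy data come from 150 mg twice daily, so activity at 100 mg is the less documented question.

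**Working it through.** **Inputs from Section 12.2.** Null rate 0.05; target rate 0.25; alpha 0.05; power 80%; 9 patients in stage 1; 9 more if at least 1 responds; success at 3 or more responses in total.

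**Success probability.** For a counted response rate t, success means at least 3 responses in 18, less the paths with none in stage 1 and at least 3 in stage 2, because the trial would have stopped:

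P(success) = P[Bin(18, t) ≥ 3] − P[Bin(9, t) = 0] × P[Bin(9, t) ≥ 3]

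**The plan's own design first.**

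- t = 0.05: 0.0581 − 0.6302 × 0.0084 = 0.0529.
- t = 0.25: 0.8647 − 0.0751 × 0.3993 = 0.8347.

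A search for the optimal two-stage design with these inputs gives 9 then 8 patients (17 in total), with the same continuation and success thresholds, exact alpha 0.0466 and power 0.812. The stated 18 is one patient more, and its exact alpha slightly exceeds 0.05. That is a separate matter; the point here does not depend on it.

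**Adding escalation.** The documents supply none of the following, so all three are assumptions: p, the response rate at 100 mg; e, the share of non-responders who escalate; q, the share of those who then respond for the first time. The counted rate is

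t = p + (1 − p) × e × q

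| p | e | q | t | P(success) |
|---|---|---|---|---|
| 0.05 | any | 0 | 0.05 | 0.053 |
| 0.05 | 0.5 | 0.05 | 0.05 + 0.95 × 0.025 = 0.0738 | 0.131 |
| 0.05 | 0.5 | 0.10 | 0.05 + 0.95 × 0.05 = 0.0975 | 0.234 |
| 0.10 | any | 0 | 0.10 | 0.246 |
| 0.10 | 0.5 | 0.05 | 0.10 + 0.90 × 0.025 = 0.1225 | 0.355 |

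For example, the third row is 0.2537 − 0.3972 × 0.0497 = 0.234.

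**What a large shift would need.** Moving the counted rate from 10% or 15% up to 25% would take P(success) from 0.246 or 0.488 to 0.835. Solving for q with half of non-responders escalating:

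- from 10%: 0.15 / (0.90 × 0.5) = 33%
- from 15%: 0.10 / (0.85 × 0.5) = 24%

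If all non-responders escalate, the figures are 0.15 / 0.90 = 17% and 0.10 / 0.85 = 12%. With half escalating, the late rate has to exceed the assumed 100 mg rate. With all escalating, it exceeds a 10% base and falls somewhat below a 15% base. Nothing in the documents supports late rates of that size.

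**The case against.** The best reply is that the formal endpoint in Section 12.1 mentions no dose and Section 12.2 speaks of the intervention. The decision rule can then be read as covering the regimen as given, escalation included. The word fixed occurs only in Section 1.1.6, is not defined there, and might mean a flat tablet dose. On that reading the trial answers a coherent question, and the fault lies in one phrase and two incomplete summaries. This stands in part: a reader might infer that the trial cannot answer its primary question at all, and the documents do not support that. They do leave the objective and the treatment plan in disagreement about what the response rate describes.

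Three further limits also stand.

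- Escalation is conditional and discretionary, so the count can mix doses but need not.
- The median time to response of 2 months in Section 2.1.8 suggests that many first responses would come before the 3 month visit. That figure is from 150 mg BID in indolent lymphoma, so it transfers only loosely, and it leaves room for later responses.
- A late response in an escalated patient might have occurred on 100 mg anyway. The documents compare no response rates between the two doses, and Section 2.1.7 reports less than dose-proportional exposure.

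All dose changes are already recorded under Section 4.1.1, so dose at first response can be derived. That makes the remedy cheap, but the plan does not yet call for the table.

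**Conclusion.** The point holds as an inconsistency between the primary objective and the treatment plan that carries through to the success count. As written, a declared success can include responses first reached on 150 mg BID and still be worded as response to a fixed dose.

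Its size cannot be fixed from the documents. With half of non-responders escalating, the modest assumptions above add 0.078 (0.131 − 0.053) to 0.181 (0.234 − 0.053) to the success probability from a 5% base, and 0.109 (0.355 − 0.246) from a 10% base. If no first response follows escalation, they add nothing. These figures treat every late response in an escalated patient as additional to the 100 mg rate.

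A reader might infer that escalation could lift the success probability from 25–49% to 83%. The arithmetic is right, but it needs the high late response rates shown above. A reader might also infer that the primary count should be cut to pre-escalation responses. That would give escalated patients a response window of about 3 months and leave the others open throughout, with the difference set by tolerance and investigator choice. It would also drop late responses that 100 mg alone might have produced.

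**What to change.** Reconcile Sections 1.1.2, 1.1.6 and 12.0 with Sections 4.1.1 and 5. Which dose rule is right is for the sponsor and investigator, and this review takes no position on it.

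If the treatment plan stands as written:

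- Word the primary objective and the conclusion as the hematologic response rate to idelalisib started at 100 mg BID with optional escalation, and state that responses count regardless of escalation.
- Tabulate the dose being taken at first response.
- Pre-specify a supportive response rate that counts only responses first reached before any escalation, and note beside it that escalated patients have a shorter response window.

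The cost is some rewording and one extra table from dose records the protocol already requires. The supportive figure may be less favourable than the primary one. Sample size and decision rule need no change on this account.

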### 1.1.7 Secondary Objectives:

- To assess progression free survival (defined as the interval from the first documentation of CR, VGPR or PR to the earlier of the first documentation of disease progression)
- To determine organ response (defined as improvement of involved organ function i.e. eGFR for kidneys, EF for heart etc.)
- To assess the safety and tolerability of idelalisib
- To measure impact on QOL of life using SF-36 assessment tool.

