### 2.1.8. Clinical Efficacy

Idelalisib has shown to be active and well tolerated in a range of B-cell malignancies (Benson 2013; Brown 2013). Idelalisib is highly active as monotherapy in CLL, FL, SLL, LPL, MZL and MCL. Responses to idelalisib are characterized by rapid and durable reductions in lymphadenopathy. Consistently positive results have been demonstrated on a number of endpoints including ORR, DOR and PFS. Idelalisib results thus far support its continued evaluation in subjects with B-cell malignancies. Most of the available clinical efficacy data is based on a dose of 150 mg PO twice daily.

Results from the 101-09 study were recently published (Gopal 2014). In this study, 125 patients with indolent NHL (including 10 patients with WM) who had not had a response to rituximab and an alkylating agent or had had a relapse within 6 months after receipt of those therapies received idelalisib at 150 mg PO BID until disease progression or withdrawal from study. The response rate was 57% with 6% CR rate. The median time to response and DOR were 2 months and 12.5 months, respectively, with a median PFS of 11 months. Based on this study, among the 10 WM patients, 1 PD, 1 SD, 6 MR and 2 PR were observed.

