#### 4.1.4 Duration of Participation

Participants will continue to take Idelalisib per-protocol until disease progression or unacceptable adverse event. Study visits will occur two weeks after starting Idelalisib, then monthly from the start of Idelalisib for three months, followed by every three months from the start of Idelalisib thereafter until disease progression or the start of another line of therapy, whichever occurs first. For patients who have responded but come off Idelalisib for reasons other than progression, they will be followed every 6 months until progression or another line of therapy. An end of study visit will take place 30 days following the last dose of Idelalisib. The duration for individuals, and duration of the study, are dependent upon disease response. We anticipate no more than 2 years duration for individual subjects. We anticipate the study will remain active for a total of 4 years including enrollment, treatment, follow-up and data analysis.

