#### 8.5 Progression-Free Survival

Progression-Free Survival (PFS) is defined as the duration of time from start of treatment to time of objective disease progression (including initiation of new therapy or death). Follow-up will continue until disease progression, which we anticipate to be no more than 2 years.

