#### **12.1 Study Design/Endpoints**

The primary endpoint of the current study is:

- To assess the hematologic overall response rate (ORR) of idelalisib in IgM-associated AL amyloid patients.

The secondary endpoints are:

- To assess the safety and tolerability of idelalisib
- To evaluate organ response
- To evaluate progression free survival
- To measure impact of idelalisib treatment on quality of life

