## 12.4 Reporting and Exclusions

All participants who met the eligibility criteria and were enrolled in the trial will be included in the main analysis of the response rate. All conclusions will be based on all eligible participants.

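### Sections 1.1.7 and 8.5 define PFS with different starting points and different patients, and no text says which definition prevails

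*Combined protocol and SAP*

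**What the plan says.** Section 1.1.7 (Secondary Objectives) lists PFS with its own definition: "defined as the interval from the first documentation of CR, VGPR or PR to the earlier of the first documentation of disease progression". The sentence ends there, so the second of the two events it promises is missing.

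Section 8.5 (Progression-Free Survival), under Measurement of Effect, says that PFS "is defined as the duration of time from start of treatment to time of objective disease progression (including initiation of new therapy or death"). It adds that follow-up runs to progression, expected within 2 years.

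Section 12.1 lists the endpoint only as "To evaluate progression free survival", with no definition or cross-reference. Section 1.1.2 says only that PFS will be assessed. Sections 12.2 to 12.4 do not mention it.

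The background in Section 2.1.8 treats duration of response (DOR) and PFS as separate quantities when it reports the indolent lymphoma study: "The median time to response and DOR were 2 months and 12.5 months, respectively, with a median PFS of 11 months".

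**The concern.** The plan applies one name to two different quantities. An analyst who follows the objective as written would report, as PFS, an interval that exists only for patients who responded. Patients who progress or die without responding are the ones a PFS summary most needs, and they would be absent. A reader comparing the result with a conventional PFS would be comparing different populations and different time origins.

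The trial is open label with a single arm. If the choice is left open, it could be made after the data are seen.

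**Working it through.** The plan states no sample size, event count or power for PFS, so there is no figure to reproduce. The check is a comparison of texts, followed by simple arithmetic for scale.

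**1. The two definitions side by side**

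| | Section 1.1.7 | Section 8.5 |
|---|---|---|
| Start | First CR, VGPR or PR | Start of treatment |
| Who has a value | Responders only | Every treated patient |
| Events | Progression, plus a second event that is missing | Progression, new therapy or death |

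**2. Would completing the 1.1.7 sentence be enough?** No. Whatever second event is supplied, a patient who never responds still has no start date. The difference in origin and population remains.

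**3. Which definition does the rest of the plan fit?**
- Section 4.1.3 groups progression, new therapy and death in one criterion for ending treatment. This fits 8.5.
- Section 5.1.1, reason 4, counts new therapy with progression. This fits 8.5.
- Section 8.2 defines progression from stable disease as well as from response, so progression without response is foreseen. This fits 8.5.
- Section 8.5 is the headed definition in the chapter on measurement.
- Section 4.1.4 points the other way: "For patients who have responded but come off Idelalisib for reasons other than progression, they will be followed every 6 months until progression". This is the only explicit off-drug schedule, and it covers responders only, so it fits 1.1.7 better.

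None of these states precedence.

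**4. Scale**

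Inputs: 18 patients (Section 1.1.5); stages of 9 and 9; alternative response probability p1 = 0.25; continue if at least 1 response in stage 1; and "the intervention would be declared successful if at least a total of 3 responses are observed during the study period" (all Section 12.2). Every enrolled patient is assumed to be treated.

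- Expected responders if all 18 enrol: 18 × 0.25 = 4.5.
- Probability of stopping at stage 1: 0.75^9 = 0.0751. Probability of reaching stage 2: 1 − 0.0751 = 0.9249.
- Expected responders allowing for that stop: 9 × 0.25 + 0.9249 × 9 × 0.25 = 2.25 + 2.08 = 4.33.
- Expected responders given that stage 2 is reached: 2.25 / 0.9249 + 2.25 = 4.68.
- Fewest responders in a successful trial: 3, and 3/18 = 17%.
- Expected number with a value under 8.5, allowing for the stop: 9 + 9 × 0.9249 = 17.3, or 18 if stage 2 fills.

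The accrual projection in Section 12.2 gives 15 patients instead of 18. On that figure the expected number of responders is 15 × 0.25 = 3.75.

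**The case against.** The strongest reply is that a competent analyst would use 8.5 anyway. It is the formal definition, its events match Sections 4.1.3 and 5.1.1, and the response criteria in 8.2 allow progression without response. This largely stands and is why the practical risk is limited. It does not remove the point: 1.1.7 is the stated objective and carries its own explicit definition, one sentence in 4.1.4 fits it, and no text resolves the conflict.

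It is also fair to say that the counts above only restate that responders are a subset, and that they depend on p1 being true. The contradiction does not rest on them.

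Four stronger readings are tempting, and the documents do not support them:
- **That 1.1.7 excludes death as an event.** The second event is missing, which does not show that it was meant to be something other than death.
- **That 1.1.7 conflicts with Section 12.4.** That section does say "All conclusions will be based on all eligible participants". But the sentence before it reads "All participants who met the eligibility criteria and were enrolled in the trial will be included in the main analysis of the response rate", so the context is the response rate and PFS is not mentioned.
- **That non-responders who stop the drug are lost to outcome follow-up.** Section 8.5, the three-monthly visits in 4.1.4 and footnote 6 of the study calendar can be read as following everyone to progression. The text is uneven, but it can be read consistently.
- **That the lack of a stated estimation and censoring method for PFS is an error of the same kind.** It is missing detail for an untested endpoint.

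**Conclusion.** The concern holds as a contradiction in time origin and population between 1.1.7 and 8.5, with an unfinished end point in 1.1.7 and no statement of precedence. The 1.1.7 interval is duration of response under the name PFS.

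Followed literally at p1 = 0.25, it would give a value for about 4 to 5 of 18 patients, and for as few as 3 in a trial that just succeeds. Section 8.5 gives a value for every treated patient. No effect in months is claimed, because the documents give no basis for one in this trial.

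PFS has no hypothesis, threshold or decision rule here. The response-rate decision, the sample size and the stage-1 stop are therefore untouched. The point should be fixed because the objective is wrong as written, but it does not threaten the trial's main conclusion.

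**What to change.** - In Section 1.1.7, delete the parenthetical definition and refer to Section 8.5. Add the same cross-reference in Section 12.1.
- State that PFS is reported for all treated patients.
- If the interval from first response is wanted, list it as a separate endpoint called duration of response, and supply the missing second event.
- Make the off-drug follow-up sentence in Section 4.1.4 consistent with the statement in 8.5 that follow-up runs to progression, so that the 8.5 endpoint can be ascertained in responders and non-responders alike.

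The cost is a few wording changes, best made before the data are analysed. If the reconciled text confirms follow-up to progression for everyone, a few off-drug patients may need additional routine blood tests. Sample size and the primary analysis do not change.
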